**Is there an immediate effect on pectoralis minor length
after performing a prone scapular retraction exercise
using typical sets and repetitions in pain free
participants?**

11/30/2023

Study Protocol with SAP

Brief Summary

Subacromial impingement is a common shoulder pathology. Participants with subacromial impingement have been shown to have decreased upward rotation, decreased posterior tipping and increased internal rotation of the scapula when compared to those with asymptomatic shoulders during arm elevation. One hypothesis for these differences in scapular kinematics is a shortened pectoralis minor. The objective of this study is to determine if there is an immediate length change of the Pectoralis Minor (PM) muscle after performing a prone scapular retraction exercise in normal participants.

Detailed Description

A convenience sample comprised of 50 healthy participants with no current shoulder pathologies will be studied. The Dependent variable will be PM length as measured by calipers in standing.

Recruited participants will fill out a consent form and then a medical history form to ensure they do not violate the exclusion criteria. Participants will then demonstrate shoulder elevation ROM to ensure they have at least 130 degrees of shoulder elevation. Participants will then receive a brief shoulder evaluation to further rule out shoulder pathology. Participants will then have their standing height measured in centimeters with a tape measure fixed against a wall. Participants will then step away from the wall and be asked to stand in their resting position. A mark will then be placed on the most medial-inferior aspect of the coracoid process and a second mark on the anterior-inferior edge of the fourth rib one index finger's width lateral to the sternum. Then a

caliper will be used to measure the distance between these marks as the participant holds a normal exhalation. This caliper will then be set aside for measurement recording once all PM measurements have been collected in order to keep the tester blinded.

The participant will then lie prone on a treatment plinth with a small towel roll under their forehead. The participant will form fists with their hands and place them on the plinth just superior to their head, fists touching the crown of their head, with their thumbs up and the ulnar side of the hand resting on the plinth with their arms relaxed so their elbows remain on the plinth. The participant will then lift their elbows off the plinth as high as possible while keeping the hands remaining on the plinth. The participant will repeat this motion for 10 repetitions, performing 3 sets of this exercise with 30 seconds rest in between each set. The participant will be instructed to not hold the end range position and be monitored throughout the exercise to make sure they are performing the exercise correctly.

The participant will then stand up and a second caliper will be used to once again measure PM length in resting standing position as above by the same tester using the same marks. Only then will the two caliper measurements be recorded and Pectoralis Minor Index (PMI) be calculated. This will conclude the testing procedure and the participant's involvement in the study.

A Paired T test will be used to analyze PM length and PMI pre-exercise versus PM length and PMI post-exercise using SPSS. The Standard error of measurement (SEM) and the minimum detectable change (MDC) will also be analyzed.

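### Pre- and post-exercise lengths are taken with two different calipers, with no balancing of their roles or common reading scale, so a constant offset between them could enter the estimated change

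*Combined protocol and SAP*

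**What the plan says.** All of this is in the Detailed Description of the combined protocol and SAP.

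- Sample: "A convenience sample comprised of 50 healthy participants with no current shoulder pathologies will be studied". There is one group and no control or no-exercise condition.
- Outcome: "The Dependent variable will be PM length as measured by calipers in standing".
- Handling of the pre-exercise reading: "This caliper will then be set aside for measurement recording once all PM measurements have been collected in order to keep the tester blinded".
- Post-exercise reading: "a second caliper will be used to once again measure PM length in resting standing position as above by the same tester", on the same skin marks.
- Recording: "Only then will the two caliper measurements be recorded and Pectoralis Minor Index (PMI) be calculated".
- Analysis: "A Paired T test will be used to analyze PM length and PMI pre-exercise versus PM length and PMI post-exercise using SPSS".
- Reliability: "The Standard error of measurement (SEM) and the minimum detectable change (MDC) will also be analyzed".

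The plan does not say which physical caliper goes first, whether the roles alternate, whether the two calipers are checked against each other or a known length, or whether the openings are read on each caliper's own scale or on one shared ruler.

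**The concern.** The caliper changes between the two readings in every participant. Pairing cancels whatever is common to both readings of one person. It does not cancel a difference between the two instruments if one of them always, or mostly, takes the first reading.

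The pre-post difference is the study's only effect estimate. An offset tied to reading order could therefore look like a length change when there is none, or hide a real one. Without a control condition, nothing else in the design would reveal it. If caliper identity is not recorded and the calipers are never compared, it cannot be separated from the exercise effect afterwards.

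**Working it through.** **Inputs.** From the plan: n = 50, one reading before and one after, paired t-test (49 df). Not in the plan, so assumed: two-sided alpha 0.05, SDd of 2 to 10 mm, offset of 0.1 to 1 mm. The plan gives no alpha, power or SD, so it has no figure of its own to reproduce.

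**Bias.** Let b be the reading of caliper B minus that of caliper A at the same opening, and q the share of participants measured with A first. When A is first, post minus pre = true change + b + random error. When B is first, b enters with the opposite sign. The mean shift is therefore

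qb - (1 - q)b = b(2q - 1).

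- Fixed roles (q = 1): the full b.
- 40/10 split (q = 0.8): 0.6b.
- 25/25 (q = 0.5): zero.

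The sample size does not appear in this expression.

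**False positives with fixed roles and no true change.** The t statistic is noncentral t with 49 df and noncentrality (b/SDd)√50. Example: b = 0.5 mm and SDd = 2 mm give 0.25 × 7.071 = 1.77, hence a 41% rejection rate.

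| Assumed offset | SDd 2 mm | SDd 3 mm | SDd 5 mm | SDd 8 mm | SDd 10 mm |
|---|---|---|---|---|---|
| 0.1 mm | 6.4% | 5.6% | 5.2% | 5.1% | 5.1% |
| 0.2 mm | 10.7% | 7.5% | 5.9% | 5.3% | 5.2% |
| 0.5 mm | 41% | 21% | 11% | 7% | 6% |
| 1 mm | 93% | 64% | 28% | 14% | 11% |

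The rate reaches 10% at an offset of 0.094 SDd: 0.19 mm if SDd is 2 mm, 0.94 mm if it is 10 mm.

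**Masking a real change.** With a true change of 0.4 SDd and a fixed-role offset in the opposite direction, power falls from 79% to 55%, 28% and 10% at offsets of 0.1, 0.2 and 0.3 SDd.

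**Effect of the role split.** False-positive rates from simulation, 100,000 trials per cell, no true change; the fixed-role row is from the noncentral t:

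| Roles and analysis | 0.1 SDd | 0.2 SDd | 0.3 SDd | 0.5 SDd |
|---|---|---|---|---|
| Fixed, paired t | 10.7% | 28.4% | 54.8% | 93.4% |
| 40/10, paired t | 7.0% | 12.5% | 22.2% | 48.8% |
| Random pick-up, paired t | 5.1% | 4.9% | 5.2% | 5.0% |
| 25/25, paired t | 4.8% | 4.5% | 4.1% | 2.9% |
| 25/25, order term added | 4.9% | 5.0% | 5.0% | 5.0% |

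Exact balance with the plain test is slightly conservative, because the offset cancels in the mean but adds to the observed SD.

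**PMI.** The index is calculated from the same readings. The plan does not define it; if it is PM length scaled by height, as the height measurement suggests, the same offset carries through.

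**SEM and MDC.** With fixed roles a constant offset leaves SDd unchanged, so an SEM or MDC built on SDd is also unchanged. If SDd were all measurement error, SEM = SDd/√2 and MDC95 = 1.96 × √2 × SEM = 1.96 SDd. An offset of 0.283 SDd (0.283/1.96 = 14% of MDC95) already gives a 50% false-positive rate. The true mean change detectable with 80% power is 0.404 SDd (0.404/1.96 = 21% of MDC95). Both lie well below MDC95, so comparing the mean change with it would not tell them apart.

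**The case against.** The bias needs three things together: one caliper systematically first, each opening read on its own scale, and an offset large enough to matter against SDd. The documents establish none of them. Setting a caliper aside and recording both measurements at the end is quite compatible with holding both openings against one ruler, in which case the problem largely disappears. If the calipers are simply picked up at random, it does not arise. All of this stands.

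The magnitude is also assumed throughout. A reader might take the 41% and 93% figures as the error rates to expect. The documents do not support that: those figures combine offsets of 0.5 and 1 mm with the smallest assumed SDd, and nothing in the plan shows that the two calipers differ by that much. Equally, the plan states no caliper type, accuracy or check from which agreement could be assumed.

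A reader might also infer that the planned SEM and MDC are bound to miss an offset. That goes too far, because the plan does not say how they are derived. A reliability exercise using both calipers, or an absolute-agreement SEM from the pre/post pair, would include a systematic shift. The pre/post version would help little: its inflation is √(1 + (b/SDd)²), about 2% at 0.2 SDd and 12% at 0.5 SDd, and it could not separate an offset from a real change.

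The two-caliper procedure is a deliberate blinding measure and should be kept. Finally, the missing control condition is the larger weakness of the design, and balancing the calipers does not touch it. That is true, but it is no reason to leave this avoidable source of error in place.

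**Conclusion.** The point holds as a conditional one. As written, the procedure allows a constant inter-caliper offset to enter the only effect estimate as b(2q-1), and neither the paired t-test nor a larger sample would remove it. It would be wrong to conclude that the study is biased: the plan neither confirms nor excludes fixed roles and separate scales, and gives no offset.

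On the assumptions stated, the consequence runs from negligible at 0.1 mm to serious when an offset of 0.5 to 1 mm meets a small SDd. The algebra is exact under its conditions; the practical size is unknown. The plan should be changed because the risk can be removed before data collection at almost no cost, and balancing roles or using one scale is a better procedure than the one described.

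**What to change.** Adopt one of the following and state it in the Detailed Description.

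1. Label the calipers A and B, use A first in a random 25 of the 50 participants from a pre-generated list, and record which caliper took each reading.
2. Or, after the second measurement, read both openings on one common scale.

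Useful low-cost addition: check both calipers against the same known lengths before and after data collection, for example 10 readings each, and report the offset.

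Optional with the first choice: analyze the post-minus-pre difference, for PM length and PMI, with a caliper-order term coded +1/-1, so that the intercept is the estimated change. The plain paired t-test under 25/25 balance already keeps false positives at or below 5%. The term restores the nominal rate for one degree of freedom, and power at a true change of 0.4 SDd moves only from 79.18% to 79.15%.

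Cost: a 50-line list and one data column, or one shared ruler, and slightly more handling. No extra participants are needed and the tester stays blinded.

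Limit: neither option removes other shifts tied to reading order. In simulation, such a shift of 0.1 to 0.5 SDd still gave 10.8% to 93.3% false positives under 25/25 balance with the order term. The lack of a control condition also remains.

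### Does reusing the pre-exercise skin marks stop the caliper change from being read as a change in pectoralis minor length?

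*Combined protocol and SAP*

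**What the plan says.** The Brief Summary gives the objective as to "determine if there is an immediate length change of the Pectoralis Minor (PM) muscle". The Detailed Description names the outcome: "The Dependent variable will be PM length as measured by calipers in standing".

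The coracoid mark is set in standing, before exercise: "A mark will then be placed on the most medial-inferior aspect of the coracoid process". At the same stage the other goes over the lower front border of the fourth rib, beside the breastbone. For the first reading a "caliper will be used to measure the distance between these marks as the participant holds a normal exhalation".

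The participant then lies prone with fists at the crown of the head and does three sets of ten lifts: "The participant will then lift their elbows off the plinth as high as possible". Afterwards the participant stands in the same resting posture and is measured again "by the same tester using the same marks". Both calipers stay unread until the end: "Only then will the two caliper measurements be recorded".

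The analysis is a paired t-test of PM length and of the Pectoralis Minor Index (PMI), before versus after. SEM and MDC are also to be reported. The plan describes no re-palpation, re-marking, check of mark against bone or no-exercise repeat reading.

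**The concern.** The plan wants the length of a muscle but records the distance between two surface marks. The two agree at the first reading, apart from palpation error. They agree at the second only if the marks still sit over the same bony points after 30 prone elbow lifts. If the skin comes to rest differently over the coracoid or rib, the caliper can show a change when the landmarks have not moved apart, or hide one when they have.

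Both planned readings use the same marks, so the data cannot separate the two explanations. PMI offers no independent check: its formula is not given, but if it is PM length scaled by the single height measurement it carries the same error. SEM and MDC do not help either. Their data source is not stated, and repeats on undisturbed marks would not pick up displacement caused by the exercise. At stake is the interpretation of the study's only outcome.

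**Working it through.** **1. What the paired difference contains.** For participant i, write D_i = L_i + m_i. D_i is the observed change, L_i the true change in coracoid-to-rib distance, and m_i the change in mark-to-bone offset along the measured line. Then mean(D) = mean(L) + mean(m). Displacement that leaves the mark-to-mark distance unchanged gives m_i = 0. Displacement that averages zero across participants adds variance but no bias. Only a systematic shift misleads.

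**2. How large a shift would matter.** The plan gives n = 50 but no SD, alpha or effect size, so there is no planned figure to reproduce. Assume a two-sided 5% test. With 49 df, t = 2.0096, and the mean must exceed 2.0096/√50 = 0.284 SD of the paired differences to be significant. If the true change is zero:

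| Assumed SD of differences | Mean shift at the significance limit | P(p<0.05), 1 mm shift | P(p<0.05), 2 mm shift |
|---|---|---|---|
| 2 mm | 0.57 mm | 0.93 | 1.00 |
| 4 mm | 1.14 mm | 0.41 | 0.93 |
| 6 mm | 1.71 mm | 0.21 | 0.64 |
| 8 mm | 2.27 mm | 0.14 | 0.41 |

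The point would matter if a systematic shift of a millimetre or two occurred. The documents do not say whether one does.

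**3. What the same-mark design buys.** Assume a caliper SD of 1 mm, a between-person SD of true change of 1.5 mm, and an error SD of λ in the distance each time both landmarks are found.

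- Same-mark change: λ cancels. SD = √(1² + 1² + 1.5²) = √4.25 = 2.06 mm. The 95% CI half-width is 0.284 × 2.06 = 0.59 mm.
- Re-palpated change: λ enters twice. SD = √(2λ² + 4.25).

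| λ (assumed) | SD of re-palpated change | 95% CI half-width |
|---|---|---|
| 1 mm | √6.25 = 2.50 mm | 0.71 mm |
| 2 mm | √12.25 = 3.50 mm | 0.99 mm |
| 4 mm | √36.25 = 6.02 mm | 1.71 mm |

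At λ = 4 mm the variance ratio is 36.25/4.25 = 8.5, so matching the same-mark precision would take about 8.5 × 50 ≈ 426 participants.

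**4. Whether a third, re-palpated reading could settle it.** The natural remedy keeps the same-mark reading as primary, re-palpates, takes one more reading, and examines the difference between the two post-exercise readings. A rule could then allow PM-length wording only if the 95% CI for that difference includes zero and rules out, in either direction, a shift as large as the reported change.

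The difference has SDr = √(2λ² + 2). This is 2.00, 3.16 and 5.83 mm for λ = 1, 2 and 4 mm. The half-width 0.284 × SDr is 0.57, 0.90 and 1.66 mm, and a reported change below roughly that size will rarely be cleared. By simulation at λ = 4 mm:

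| True change | Mark shift | PM-length wording kept |
|---|---|---|
| 1 mm | 0 | 0.3% (the planned test is significant in 92%) |
| 2 mm | 0 | 33% |
| 3 mm | 0 | 86% |
| 1.5 mm | 1.5 mm | about 40% |
| 0 | 3 mm | about 2% |

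The shifted rows also assume a between-person SD of mark shift of 0.5 mm. A null result can never be cleared, because no interval fits inside limits that shrink to zero. The rule performs well only at the extremes: a large change with no shift, or a change that is all shift.

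**The case for a change.** The best case for acting is that this concerns the only outcome and the one claim the study exists to make. A third caliper would be cheap and would fit the existing routine of leaving calipers unread. It would leave n and the t-test alone. On the text this is right: nothing in the plan tests the assumption, and nothing else in it answers the point.

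What does not stand is that the extra reading would resolve it. A gap between the two post-exercise readings could come from mark movement, fresh landmark error, tester expectation or the later time of measurement. It would show that the methods disagree, not why. The case against it is also sensitive to λ. If palpation were repeatable to about 1 mm, the check's half-width (0.57 mm) would be close to that of the planned test (0.59 mm), and the check would be more useful. The documents give no λ, so neither end of the range can be claimed.

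The plan also does something to limit the problem. Both readings are taken in resting standing, the second repeats the procedure of the first, including the held exhalation, and the tester is the same. This limits differences due to posture and breathing. It does not exclude displacement from the exercise itself.

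**Conclusion.** No change to the plan is needed. The same-mark reading rests on one unverified assumption: that displacement between mark and bone along the measured line averages zero across participants. The documents neither show nor suggest a breach, and its size cannot be estimated from them. In return the design removes landmark-finding error from the paired difference. Under the assumed SDs this narrows the 95% CI half-width from between 0.71 and 1.71 mm (λ from 1 to 4 mm) to 0.59 mm. That is a fair trade for a single-group before-and-after study.

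The alternatives gain little. A re-palpated reading used to decide the wording would mostly reflect palpation noise unless λ is near 1 mm, and it could never clear a finding of no change. Rewording the outcome as a distance between surface marks would alter no result, and the outcome is already defined as a caliper measurement in standing. A sensible analyst keeps the readings and the t-test as planned. When calling the result PM length, the report should say that mark position was not rechecked after exercise. All millimetre SDs and shifts here are assumptions; only n = 50 and the measurement sequence come from the documents.
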